3.3 Number of Subjects

Participants in this clinical investigation shall be referred to as "subjects".

There will be approximately 900 subjects randomized in this study. Justification for the sample size can be found in Section 10.2 Sample Size Considerations.

3.4 Replacement of Subjects

There will be no replacement for randomized subjects. Enrollment will continue until the target number of subjects (Section 3.3) have been randomized to IP, regardless of the number of subjects starting lipid stabilization on atorvastatin.

3.5 Estimated Study Duration

3.5.1 Study Duration for Subjects

After signing the informed consent, subjects should be randomized within 8 weeks. Including the screening, study treatment, and follow-up, the maximal total duration of study participation for a subject on QM IP schedule will be 20 weeks or approximately 5 months. For a subject on Q2W IP schedule, maximal study duration will be 22 weeks or approximately 5 ½ months, including the contact by the site at week 14 to obtain potential AE, **ADE**, and SAE information.

3.5.2 End of Study

The end of the study (primary completion) is defined as the last day on which a randomized subject completes the end-of-study visit or phone follow-up (week 12 for subjects on QM IP administration; week 14 for subjects on Q2W IP administration) or terminates the study early, whichever is later.

4. SUBJECT ELIGIBILITY

Investigators will be expected to maintain a screening log of all potential study

candidates that includes limited information about the potential candidate (eg, date of screening).

Before any_study-specific activities/procedure, the appropriate written informed consent must be obtained (see Section 11.1).

4.1 Inclusion and Exclusion Criteria

4.1.1 Inclusion Criteria

- 101 Subject has provided written informed consent.
- 102 Male or female, \geq 18 to \leq 80 years of age at signing of informed consent.
- 103 Type 2 diabetes, defined as receiving pharmacologic treatment for type 2 diabetes for ≥ 6 months prior to screening, with stable diabetes therapy prior to randomization to IP and not expected to change during the duration of study participation. Stable diabetes therapy is defined as no new agents added, no dose change of any oral antihyperglycemic drug within 2 months, and daily insulin dose not changed by > 25% and > 25 units within 1 month prior to randomization
- 104 Lipid-lowering therapy status (eg, not receiving any therapy or receiving any statin, ezetimibe, bile-acid sequestering resin, stanols, probucol, omega 3 fatty acids or niacin) must be unchanged for ≥ 4 weeks prior to LDL-C screening.
- 105 Subjects receiving statin therapy at screening must have a fasting LDL-C at screening of \geq 100 mg/dL (2.6 mmol/L) as determined by central laboratory.
- 106 Subjects not receiving statin therapy at screening must have a fasting LDL-C at screening of \geq 130 mg/dL (3.4 mmol/L) as determined by central laboratory.
- 107 Fasting triglycerides \leq 400 mg/dL (4.5 mmol/L) by central laboratory at screening.

4.1.2 Exclusion Criteria

- 201 Receiving 20 mg atorvastatin QD monotherapy for approximately 16 weeks is medically contraindicated or inappropriate based on opinion of investigator.
- 202 NYHA III or IV heart failure, or last known left ventricular ejection fraction < 30%.
- 203 Uncontrolled cardiac arrhythmia defined as recurrent and highly symptomatic ventricular tachycardia, atrial fibrillation with rapid ventricular response, or supraventricular tachycardia that is not controlled by medications, in the past 6 months prior to randomization.
- 204 Myocardial infarction, unstable angina, percutaneous coronary intervention (PCI), coronary artery bypass graft (CABG) or stroke within 6 months prior to randomization.
- 205 Planned cardiac surgery or revascularization within 6 months after randomization.
- 206 Type 1 diabetes or poorly controlled type 2 diabetes (HbA1c > 10.0 % at screening and at lipid stabilization or not on stable pharmacologic therapy for

type 2 diabetes. Stable therapy is defined as no new agents added, no dose change of any oral antihyperglycemic drug within 2 months, and daily insulin dose not changed by > 25% and > 25 units within 1 month prior to randomization.

- 207 Uncontrolled hypertension defined as sitting systolic blood pressure (SBP)
 > 160 mmHg or diastolic BP (DBP) > 100 mmHg (see Section 7.7.1 regarding repeat measurement).
- 208 Subject is unwilling or unable to discontinue between start of lipid stabilization with 20 mg/day atorvastatin and end of study (week 12 for QM and week 14 for Q2W subjects) the following drugs or supplements: red yeast rice, niacin (> 200 mg/day), > 1000 mg/day omega-3 fatty acids (eg, Docosahexaenoic acid [DHA] and eicosapentaenoic acid [EPA], prescription and non-prescription combined), and all other prescription lipid-regulating drugs (eg, fibrates and derivatives, ezetimibe, bile-acid sequestering resin, stanols, or probucol) except study-provided atorvastatin.
- 209 Subject has taken a cholesterylester transfer protein (CETP) inhibitor in the last 12 months prior to randomization, such as: anacetrapib, dalcetrapib or evacetrapib.
- 210 Treatment in the last 2 months prior to screening and lipid stabilization assessments with any of the following drugs: systemic cyclosporine, systemic steroids (eg, intravenous [IV], intramuscular [IM], or oral [PO] administration), vitamin A derivatives and retinol derivatives for the treatment of dermatologic conditions (eg, Accutane); (Note: vitamin A in a multivitamin preparation is permitted).
- 211 Hyperthyroidism or hypothyroidism as defined by thyroid stimulating hormone (TSH) below the lower limit of normal (LLN) or > 1.5 times the upper limit of normal (ULN), respectively, at screening.
- 212 Moderate to severe renal dysfunction, defined as an estimated glomerular filtration rate (eGFR) < 30 mL/min/1.73m² at screening.
- 213 Persistent active liver disease or hepatic dysfunction, defined as aspartate aminotransferase (AST) or alanine aminotransferase (ALT) > 2 times the ULN as determined by central laboratory analysis at screening or lipid stabilization assessments.
- 214 Creatine kinase (CK) > 3 times the ULN at screening or lipid stabilization assessments.
- 215 Known active infection or major hematologic, renal, metabolic, gastrointestinal or endocrine dysfunction (except diabetes).
- 216 Deep vein thrombosis or pulmonary embolism within 3 months prior to randomization.
- 217 Female subject who has either (1) not used (an) acceptable method(s) of effective birth control (see below) for at least 1 month prior to screening and (2) is not willing to inform her partner of her participation in this clinical study and to use such (an) acceptable method(s) of effective birth control during treatment with IP (evolocumab or placebo) and for an additional 15 weeks after the end of treatment with IP (evolocumab or placebo), unless the female subject is permanently sterilized or postmenopausal (see below);

- A female is considered of childbearing potential unless **permanently** sterilized or postmenopausal with menopause defined as:
 - 12 months of spontaneous and continuous amenorrhea in a female
 ≥ 55 years old, or
 - 12 months of spontaneous and continuous amenorrhea with a follicle-stimulating hormone (FSH) level > 40 IU/L (or according to the definition of "postmenopausal range" for the laboratory involved) in a female < 55 years old
 - unless the subject has undergone bilateral oophorectomy
- acceptable methods of preventing pregnancy include not having intercourse, (true sexual abstinence), surgical contraceptive methods - (vasectomy of the male partner or bilateral tubal ligation/occlusion), use of hormonal birth control methods (pills, shots/injections, implants, or patches), intrauterine devices (IUDs), or two (2) barrier methods (each partner must use one barrier method) and at least one of the barrier methods must include spermicide - males must use a condom with spermicide; females must choose either a diaphragm with spermicide, OR cervical cap with spermicide, OR contraceptive sponge with spermicide. Note: a male and female condom cannot be used together due to the risk of tearing.
 - Note: If additional medications are given during treatment which may alter the contraceptive requirements (these additional medications may require an increase in the number of contraceptive methods and/or length of time that contraception is to be utilized after the last dose of protocol-required therapies) the investigator is to discuss these changes with the study subject.
- 218 Subject is pregnant or breast feeding, or planning to become pregnant or planning to breastfeed during treatment with IP (evolocumab or placebo) and/ or within 15 weeks after the end of treatment with IP (evolocumab or placebo).
- 219 Malignancy (except non-melanoma skin cancers, cervical in-situ carcinoma, breast ductal carcinoma in situ, or stage 1 prostate carcinoma) within the last 5 years prior to screening.
- 220 Subject has previously received evolocumab or any other investigational therapy to inhibit PCSK9.
- 221 Currently receiving treatment in another investigational device or drug study, or less than 30 days since ending treatment on another investigational device or drug study(s) or planning to receive other investigational procedures while participating in this study.
- 222 Subject has known sensitivity to any of the active substances or their excipients to be administered during dosing, eg, carboxymethylcellulose, or atorvastatin.
- 223 Subject likely to not be available to complete all protocol-required study visits or procedures, or unreliability as a study participant (eg, alcohol or other drug abuse in the past year or psychosis), to the best of the subject's and Investigator's knowledge.
- History or evidence of any other clinically significant disorder, condition or disease that, in the opinion of the Investigator or Amgen physician, if consulted,

would pose a risk to subject safety or interfere with the study evaluation, procedures or completion.

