End of study / Primary completion date	The end of the study / primary completion date is defined as the last day on which a randomized subject completes the end-of-study visit or phone follow-up (week 12 for subjects on QM IP administration; week 14 for subjects on Q2W IP administration) or terminates the study early, whichever is later

Abbreviation or Term	Definition/Explanation
End of study for individual subject	Defined as the last day that protocol-specified procedures are conducted for an individual subject or day the subject ends study early. Subjects will complete the study at week 12 (subjects on QM IP administration) or week 14 (subjects on Q2W IP administration).
End of treatment	Defined as the last assessment for the protocol-specified treatment phase of the study for an individual subject
EOS	End-of-study (for the individual subject)
EPA	Eicosapentaenoic acid
FAS	Full analysis set
FSH	Follicle-stimulating hormone
GCP	Good Clinical Practice
HDL-C	High density lipoprotein cholesterol
HepG2 cells	Human hepatocellular carcinoma cell line
HR	Heart Rate
hsCRP	High sensitivity CRP
IBG	Independent Biostatistical Group
ICF	Informed consent form
ICH	International Conference on Harmonization
IFU	Instructions for Use
IM	Intramuscular
INR	International normalized ratio
IRB	Institutional Review Board
IP	Investigational product
IPIM	Investigational Product Instruction Manual
IVRS/IWRS	Interactive Voice Response System / Interactive Web Response System
IV	Intravenous
LDH	Lactate dehydrogenase
LDL-C	Low-density lipoprotein cholesterol
LDLR	LDL receptor
LH	luteinizing hormone
LLN	Lower limit of normal
LOF	Loss of function
Lp(a)	Lipoprotein(a)
MedDRA	Medical dictionary for regulatory activities
Monthly	Defined as every 4 weeks with a window of \pm 3 days. For practical considerations, study visits are scheduled based on a weekly calendar with a window of +/- 3 days for each visit, thus dosing intervals are allowed to be up to 31 days for the QM regimen.

Abbreviation or Term	Definition/Explanation
MMTT	Mixed meal tolerance test
NASH	Nonalcoholic steatohepatitis
PCI	Percutaneous coronary intervention
PCSK9	Proprotein convertase subtilisin/kexin type 9
PO	Oral administration
QM	QM is defined as every 4 weeks with a window of \pm 3 days for each visit, thus dosing intervals are allowed to be up to 31 days for the QM regimen.

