3. EXPERIMENTAL PLAN

3.1 Study Design

This is a phase 3, multicenter, double-blind, randomized, stratified, placebo-controlled study of evolocumab for diabetic subjects with hyperlipidemia or mixed dyslipidemia. After undergoing screening procedures, including laboratory assessments and a screening placebo injection, approximately 900 subjects meeting eligibility criteria and completing at least 4 weeks of lipid stabilization on atorvastatin 20 mg QD will be randomized 2:2:1:1 into the following treatment arms:

- evolocumab SC 140 mg Q2W and atorvastatin PO 20 mg QD
- evolocumab SC 420 mg QM and atorvastatin PO 20 mg QD
- placebo SC Q2W and atorvastatin PO 20 mg QD, or
- placebo SC QM and atorvastatin PO 20 mg QD.

The sample size for each of the evolocumab plus atorvastatin dosing regimens will be approximately 300 subjects. The sample size for each of the placebo plus atorvastatin dosing regimens will be approximately 150 subjects.

Randomization into the 4 treatment groups will be stratified by entry statin therapy (no statin use vs non-intensive statin use vs intensive statin use [see Appendix D]) and by the site's geographic region. Treatment and follow-up period will be 12 weeks with an additional phone call or other subject contact at week 14 for subjects receiving IP Q2W.

Evolocumab and placebo SC will be administered at the study site or appropriate non-investigator site settings, eg, at the subject's home, per protocol Section 6 and Section 7 by spring-based prefilled autoinjector/pen (prefilled Al/Pen) for subjects receiving IP Q2W and by 3.5 mL Personal Injector for subjects receiving IP QM. The dose frequencies of Q2W and QM will not be blinded but the identity of IP (evolocumab or matching SC placebo) will be blinded. Post-IP treatment central laboratory results of the lipid panel, ApoA1, ApoB100, ApoB48, free fatty acids, chylomicrons, lipoprotein(a), PCSK9, insulin, proinsulin, C-peptide, glucagon, IL-6, adiponectin, vitamin E, PK, and high sensitivity C-reactive protein (hsCRP) will be blinded until unblinding of the clinical database and will not be reported to the investigator post-screening. Investigators should not perform non-protocol testing of these analytes during a subject's study participation and until at least 12 weeks after last IP administration, or the subject's end of study, whichever is later.

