6.2.1.2 Dosage Adjustments, Delays, Rules for Withholding or Restarting, Permanent Discontinuation

There will be no dose adjustments in this study. If, in the opinion of the investigator, a subject is unable to tolerate a specific dose of IP, that subject will discontinue IP but will continue to take atorvastatin and return for all other study procedures and measurements until the end of the study.

If a subject is late for administration of IP, administration should occur as soon as possible. A QM dose of IP should not be administered within less than 7 days of a previous dose. If a QM subject arrives for a visit with IP administration and IP was administered within the prior 7 days, the dose should not be administered but all other study procedures should be conducted. Administration of IP should occur as soon as possible but at least 7 days after the previous administration. Not more than 2 Q2W doses should be administered within any 7-day period. If a Q2W subject arrives for a visit with IP administration and more than 1 dose of IP was administered within the prior 7 days, the dose should not be administered but all other study procedures should be administered but all other a visit with IP administration and more than 1 dose of IP was administered within the prior 7 days, the dose should not be administered but all other study procedures should be completed. Administration of IP should occur as soon as possible but at least 7 days after the most recent previous administration.

Subjects who completely miss a dose of IP will continue in the study and receive the next dose of IP per their schedule of administration.

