6.9 Excluded Treatments and/or Procedures During Study Period

The following treatments are not permitted during the study:

- prescription lipid regulating medications other than fish oil (omega-3 fatty acids) and study-provided atorvastatin, eg, fibrates and derivatives, ezetimibe, bile-acid sequestering resin, stanols, or probucol
- red yeast rice
- niacin > 200 mg/day
- omega-3 fatty acids (eg, DHA and EPA combined) > 1000 mg/day
- other drugs (besides those mentioned above) that significantly affect lipid metabolism (eg, systemic cyclosporine, systemic steroids [IV, IM, or PO; *Note: hormone replacement therapy is permitted*], vitamin A derivatives and retinol derivatives for the treatment of dermatologic conditions [eg, Accutane; *Note: Vitamin A as part of a multivitamin preparation is permitted*]).
- prescribed amphetamines, or amphetamine derivatives, and weight loss medications.
- Other investigational therapies than evolocumab

The following treatments are not recommended because of their potential impact on metabolism of certain statins:

medications or foods that are known potent inhibitors of CYP3A (eg, Itraconazole, ketoconazole, and other antifungal azoles, macrolide antibiotics erythromycin, clarithromycin, and the ketolide antibiotic telithromycin, HIV or HCV protease inhibitors, antidepressant nefazodone and grapefruit juice in large quantities (> 1 quart daily [approximately 1 Liter]) should not be used during the study.

Should there be a clinical need to prescribe one of these treatments, the investigator should call the Amgen Medical Monitor to discuss.

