QM IP on-site or in non-investigator site setting						Х					

Table 1. Schedule of Assessments

Page 2 of 2

Page 43 of 90

a D1 = day of first administration of IP; a visit window of ± 3 days applies to all other visits; atorvastatin will be taken orally every day for ≥ 4 weeks of lipid stabilization before randomization and then continuously until the week 12 visit; atorvastatin should be taken every day at about the same time

^b subjects on Q2W IP schedule; subject is being contacted by the site at week 14, eg, by phone call

^c only AEs possibly related to study procedures and ADEs/SAEs are collected during the screening and lipid stabilization period

d only if a visit to the study site is performed instead of IP administration at a non-investigator site location

e randomization should be on day 1 or as close as possible and must not be earlier than 5 days prior to day 1

^f blood samples must be taken prior to IP administration, if applicable

9 if subject is not fasting on day 1, reschedule; if subject is not fasting after day 1, do all procedures except fasting labs and IP administration, if applicable; schedule another visit, if possible within the visit window for fasting labs and IP administration

^h postprandial blood draw at 120 ± 10 mins after standardized mixed meal (see Section 7.7.6) for all subjects; additional postprandial blood draws at 60 ± 10 mins and 180 ± 10 mins for subjects participating in the MMTT Extended Timepoints Substudy (see Section 7.7.7). Other markers for metabolic status may be assessed as well.

ⁱ if the subject consented to pharmacogenetics analyses, deoxyribonucleic acid (DNA) will be extracted from some of the blood samples, eg, biomarker samples

J HCV antibodies only in subjects at high risk for, or with history of, HCV infection, or born between 1945 and 1965 (see Section 7.2.1.1) or if ALT or AST > 2x ULN at any time during screening; viral load only in subjects positive for HCV

k pregnancy testing in females of childbearing potential, FSH only if applicable per Section 4.1.2, exclusion 217

Applies to subjects in China only: steroid analytes include cortisol, adrenocorticotropic hormone, estradiol, testosterone, luteinizing hormone (LH), and FSH

^m timepoints of atorvastatin dispensation and tablet count may vary regionally and differ from the timepoints shown here

Refer to Sections 7.2 through 7.7 and the applicable supplemental laboratory manual, ECG manual, and IPIM for detailed study procedures.

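### For Q2W subjects, study atorvastatin stops at week 12 while exclusion 208 bars other lipid-regulating drugs to week 14; close the two-week gap in statin cover

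*Protocol*

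**What the plan says.** **When study atorvastatin stops.** Protocol Table 1, footnote a, has it taken daily during lipid stabilization "and then continuously until the week 12 visit", with no distinction between regimens. The table shows the last dispensation at week 8 and the last tablet count at week 12; footnote m allows regional variation. Exclusion 201 is worded for a similar span: "Receiving 20 mg atorvastatin QD monotherapy for approximately 16 weeks is medically contraindicated".

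**How long other drugs are barred.** Exclusion 208 turns away subjects who will not stop listed drugs between the start of lipid stabilization and "end of study (week 12 for QM and week 14 for Q2W subjects) the following drugs or supplements". The list takes in every prescription lipid-regulating drug apart from the trial's own atorvastatin. Section 6.9, the rule for conduct on study, bars "prescription lipid regulating medications other than fish oil (omega-3 fatty acids) and study-provided atorvastatin" for the duration of the study and gives no week. Section 6.3 requires any permitted lipid-lowering drug to stay unchanged throughout participation.

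**When the study ends.** The glossary and section 3.5.2 end it at week 12 for QM subjects and week 14 for Q2W subjects. Section 3.1 puts it differently: "Treatment and follow-up period will be 12 weeks with an additional phone call or other subject contact at week 14". Under section 7.2.3 the week 14 contact collects only AEs, ADEs and SAEs.

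Neither document says what statin, if any, a Q2W subject should take between weeks 12 and 14.

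**The concern.** Taken together, footnote a and exclusion 208 have the one exempt statin stop two weeks before the bar on all others is lifted. This happens in the Q2W arms only. A site that follows both texts must choose between a short statin lapse, a possible protocol deviation, and a call to the medical monitor.

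These subjects have type 2 diabetes and entered with LDL-C of at least 100 mg/dL on a statin or 130 mg/dL off one. The protocol's own background section cites statin benefit in diabetes. No lipid sample remains to be protected after week 12, so the lapse would serve no measurement purpose. What is at stake is a small matter of care and clear instructions, not the trial's conclusions.

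**Working it through.** **Inputs.** Scheduled day = 7 × week + 1 (SAP Appendix A). Visit window ±3 days (Table 1, footnote a). Last IP dose at week 8 for QM and week 10 for Q2W (Synopsis, Procedures). Q2W arms of 300 and 150, with 2% never dosed (protocol 10.2). IP exposure runs to the last dose plus 28 days (QM) or 14 days (Q2W) (SAP 6.3).

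**1. The plan's own durations (section 3.5.1).** 8 + 12 = 20 weeks for QM and 8 + 14 = 22 weeks for Q2W. Both reproduce, so the two extra Q2W weeks are intended.

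**2. Length of the gap.**
- Week 12 is day 85 and week 14 is day 99: 99 − 85 = 14 days.
- If only the week 12 visit moves: 99 − 88 = 11 to 99 − 82 = 17 days.
- If the week 14 contact also moves by ±3 days (assumption): 96 − 88 = 8 to 102 − 82 = 20 days.
- For QM, the stop and the end of study are the same visit, so the gap is 0.

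**3. Number of subjects.** 300 + 150 = 450 randomized; 450 × 0.98 = 441 dosed. The plan gives no rate for stopping atorvastatin or leaving before week 12. Assuming 0 to 15%, the count is 441 down to 441 × 0.85 = 374.85, about 375.

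**4. Is a week 12 stop consistent with exclusion 201?** 4 + 12 = 16 weeks; 4 + 14 = 18 weeks. The stated 16 fits a week 12 stop, but only loosely. Stabilization lasts at least 4 weeks and randomization may come up to 8 weeks after consent, so total atorvastatin time can exceed 16 weeks anyway.

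**5. Timing of IP exposure and follow-up.**
- Nominal exposure ends on day 57 + 28 = 85 (QM) and day 71 + 14 = 85 (Q2W).
- Follow-up after the last dose is 85 − 57 = 28 days (QM) and 99 − 71 = 28 days (Q2W).

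Exposure ends together in both regimens, and the week 14 contact gives both the same four-week tail for adverse events.

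**6. Efficacy.** The last scheduled lipid sample is at week 12, and its SAP analysis window runs to day 91. A statin started only after that sample, including a rescheduled one, cannot enter any co-primary or co-secondary endpoint. No input to the power calculation changes.

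**The case against.** **The week 12 reading of section 6.9.** Exclusion 208 is an entry criterion about willingness, and section 6.9 has no end date. Sections 3.1, 7.2 and 7.2.2 describe a 12-week treatment period, and Table 1 places week 14 under a phone column outside it. On that reading nothing is barred after week 12. This has weight. Against it, exclusion 208 names week 14, the glossary ends the Q2W study there, and section 7.2.1.2 refers to exclusion 208 and section 6.9 together when it says what must be stopped. The conflict is unresolved rather than proved.

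**Routes already in the text.**
- Section 6.9 closes with "Should there be a clinical need to prescribe one of these treatments, the investigator should call the Amgen Medical Monitor to discuss". It follows the CYP3A inhibitor list, so its reach to lipid drugs is arguable, and it only prompts a discussion.
- Section 6.2.1.2 says a subject who cannot tolerate IP "will continue to take atorvastatin and return for all other study procedures and measurements until the end of the study". That covers one subgroup, and it is unclear whether the end point applies to the tablets.
- Section 6.4 allows an alternative statin only for severe muscle symptoms.
- Leftover study tablets are not forbidden, but the dosing instruction has ended.

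**External documents.** Atorvastatin dosing follows the IPIM, an external manual. Neither it nor the study schema figure was available here; either may settle the matter.

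**A reason for week 14.** Equal 28-day tails make the later contact coherent, and holding background therapy fixed to the end of adverse event collection would fit that. The documents do not give this as the reason. It would also argue for continuing atorvastatin, not for stopping it at week 12.

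**Conclusion.** The inconsistency stands as a minor patient-care point. In the protocol and SAP, Q2W subjects still on atorvastatin at week 12 reach its scheduled stop a nominal 14 days (8 to 20 with windows) before the bar in exclusion 208 ends, with no clearly permitted statin in between. It concerns about 375 to 441 subjects under the assumptions shown. No clinical effect size is claimed.

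A reader might infer more than the text supports:
- **That the protocol mandates a statin lapse.** It does not say so; section 6.9 is undated and the IPIM may address it.
- **That 441 people lose their usual statin.** The count includes subjects who entered on no statin and have none to resume. The documents give no split by entry statin group.
- **That results are compromised.** Efficacy, power and the comparison of evolocumab with placebo within Q2W are untouched.
- **That the 16 weeks in exclusion 201 settles the stop date.** It is loose support only.

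**What to change.** Amend section 6.9, exclusion 208 and Table 1 footnote a together, so that statin cover is continuous for Q2W subjects. Either option works.

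**(a) Continue atorvastatin 20 mg to the week 14 contact.** Background therapy then stays constant through the period in which treatment-emergent events are counted. Cost: up to 441 × 14 = 6,174 more tablets at the nominal interval (441 × 20 = 8,820 if everyone is supplied for the widest window), and exclusion 201 changed to about 18 weeks (4 + 14). Because week 14 is normally a phone call, the last tablets could not be counted on site.

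**(b) End the statin bar once the week 12 fasting samples are drawn, including any rescheduled sample.** A usual-care statin may then be started or resumed. Key the release to the sample rather than the visit, because the week 12 lipid window runs to day 91. Add a matching clause to section 6.3. Record concomitant therapy at the week 14 contact in Table 1 and section 7.2.3; section 6.6 already collects it to the end of study, yet that Table 1 cell is blank. Cost: a few sentences and one table cell, with no extra drug, visit or sample.

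The downside of (b) is that a newly started statin, at any dose, could contribute to the muscle- or liver-related events summarized under SAP 10.6.1 in the last two Q2W weeks. It would be permitted equally in both blinded Q2W arms, but QM subjects would have no such period. The on-treatment summary is largely spared: exposure nominally ends on day 85. Overlap is at most 88 − 82 = 6 days, when the last dose is 3 days late (74 + 14 = 88) and the week 12 visit 3 days early (day 82).

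Under either option, keep the section 7.7.5 restriction on lipid testing. No efficacy analysis changes.
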